## **8.0 Procedures Involved:**

The standard TNEC 40-hour workbook will be used in both the intervention and control classes.

In the intervention, trainees will be provided with an Oculus VR headset to complete virtual reality modules based on activities covered in the TNEC 40 hour course workbook. In control classes, trainees will complete all of the activities following standard practice which includes filling out sheets, reviewing 2D photographs, and reviewing slides. VR modules will last no longer than 1-5 minutes in length, which is a comparable length to the time allowed for students in control classes to complete their assigned tasks. There will be no differences in content provided between cases and controls. We are examining the effect of a difference in delivery mechanism and interaction with the content to enhance retention, understanding, and performance.

VR modules will be provided intermittently throughout the 40 hour course. Each course is required to be 40 hours in length by the OSHA standard.

All evaluations and assessments of trainees will take place at the same sequence between cases and controls.

Outcomes measured include student accuracy on the TNEC HAZWOPER performance instruments including; 1) the 40 Hr HazWoper Course Workbook, 2) the Toxic Properties Activity, 3) The New England Consortium Health and Safety Training Survey, 4) System Usability Scale (SUS), 5) Occupational Self-

Efficacy Scale - Short Form (OSS-6), 6) iGroup Presence Questionnaire (IPQ), 7) Flow State Scale (FSS), 8) UX for VR Questionnaire, and 9) NASA-TLX

We will first run a two-month pilot to estimate ICC, the intraclass correlation coefficient. We will use ICC to determine effect size for the following 12-month study (see Figure 10). Using this calculation, we will determine expected effect size from the more extensive 12-month portion of the evaluation effort.

Prior to analysis of the 12-month effort, we will use matching techniques based on trainee and trainer characteristics. We will use pretest matching criteria based on trainee cohort population characteristics and prior knowledge ascertained through pre-HAZWOPER training registration information.

[figure not shown]
[figure not shown]

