We will match cases and controls using Euclidian distance between intervention and control samples rather than propensity score matching to find the best match to mitigate risk of confounding due to low sample size following the guidance of [name] (King, G. and Nielsen, R., 2019. Why propensity scores should not be used for matching. *Political Analysis*, 27(4), pp.435-454.). We will compare how these modules enhance student performance across TNEC HAZWOPER performance instruments including; 1) the 40 Hour HAZWOPER Course Workbook, 2) the Toxic Properties Activity, 3) The New England Consortium Health and Safety Training Survey, 4) System Usability Scale (SUS), 5) Occupational Self-Efficacy Scale - Short Form (OSS-6), 6) iGroup Presence Questionnaire (IPQ), 7) Flow State Scale (FSS), 8) UX for VR Questionnaire, and 9) NASA-TLX

We will compare how these modules enhance performance through a t-test.

[figure not shown]
Intervention VR modules will be based on the existing activities within the 40 Hour HAZWOPER Course Workbook and the field exercise including:

Module 1 Duration: 5 Minutes	Activity 3-A What's on the Site?
------------------------------------	----------------------------------

[figure not shown]
Instrument	
3.1 CHEMICAL HAZARDS - 3 • Pg 4
 
ACTIVITY3-A
 
WHAT'S ON THE SITE?
 
Purpose: To start developing a list of clues that can be used to decide if hazardous chemicals are present on site. To get you thinking about what you need to know in order to work safely on site. To stress the importance of information and knowing where to get it.
 
Task: As a group, answer questions 1-3 using the following information: the site description below, the site map on pg. 5, and the photographs in your site packet. Numbers on the site map correspond to photo numbers. The arrows indicate the direction from which the photo was taken.
 
Site Description: Bright Corporation was a small metal plating company located on a 2 acre site. It operated between 1955 and 1992. The company was engaged in plating and painting of small metal parts. A lead acid battery manufacturer occupied the site between 1992 and 1995. The site has been abandoned for six months.
 
 
1. What clues suggest that chemical hazards may be present?
 
2. What else would you like to know about this site before entering?
 
3. Where would you go for this information?
 

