IMPRINT Intervention (Virtual Environment)	

[figure not shown]
Control Part A	
Control Part B	
Module 2 Duration 5 Minutes	Activity 11-A Controlling the Site

Instrument	
DANGER HAZARDOUS WASTE 3.1 Ch. 11 • Pg 13
 
ACTIVITY 11-A
 
CONTROLLING THE SITE
 
PURPOSE: To review the health & safety issues to be considered when developing a site control program.
 
TASK: You are in charge of buried drum removal at the Bright Corporation site. Contaminants include acids and bases, flammable solvents, chlorinated organic solvents, and metals. Using the site map on page 15 and the job description below, answer the questions on the next page.
 
 
• Drums are being unearthed manually using shovels.
 
• They are removed from the pit using an excavator with a drum grappler attached.
 
• Drums are then moved manually, using drum dollies, to the first staging area for opening and sampling.
 
• They are then moved to final staging area with dollies to await bulking and removal.
 
• Emptied drums are crushed before removal.
 
• The excavation has had problems with water build up. The water is pumped using a gasoline pump to a holding area for testing and later removal.
 
• Workers entering the excavation and workers in the drum opening area are in level B protection. Workers in sampling area in level C. All others in the exclusion zone are in level D protection.
 

IMPRINT Intervention (Virtual Environment)	

Control	 
ACTIVITY 11- A (continued)
 
DANGER HAZARDOUS WASTE
 
3.1 Ch. 11 • Pg 15
 
Site Plan Labels:
 
 
EXCAVATION
 
SPOILS PILE
 
EXCAVATOR w/ SPREADER
 
CHANLINK FENCE
 
EQUIPMENT DECON
 
DRUM CRUSHER
 
PERSONNEL DECON
 
SUPPORT ZONE TRAILER
 
RESERVOIR
 
PUMP
 
BUILDING
 
BUILDING
 
BUILDING
 
PREVAILING WIND
 
W-E
 
N
 
S
 
HOT ZONE
 
WARM ZONE
 
COLD ZONE
 

Module 3 Duration 3 Minutes	Decontamination Line Ordering and Field Exercise

Instrument (field training exercise/ evaluation)
		

IMPRINT Intervention (Virtual Environment)
		

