### ACTIVITY 3-B USING THE NIOSH GUIDE: CHEMICAL PROPERTIES

**Purpose:** To learn to how to look up information in the NIOSH Pocket Guide to Chemical Hazards. To help students recognize when chemicals have hazardous properties.

**Task:** Using the NIOSH Pocket Guide, fill in the table on page 41. (Write "NA" if the chemical property does not apply.) Do not look up each chemical yourself. Have each group member look up a couple of chemicals, then share the results. Answer the following questions about each chemical.

[figure not shown]
1. Does the chemical present a fire/explosion hazard ?
2. Is the chemical likely to form high vapor concentrations ?
3. Is the vapor/gas lighter or heavier than air ?  
(Remember : the molecular weight of air is 29. See page 30.)
4. Do you have any other concerns about the chemical ?

[figure not shown]
Continued on the next page

3.1 Ch. 3 • Pg 39

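### Workbook Activities 3-A and 3-B are printed as group tasks but counted as student accuracy, so their scores are neither individual nor independent for the planned t-test

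*Combined protocol and SAP*

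**What the plan says.** Section 8.0 (Procedures Involved) of the combined protocol and SAP defines the outcome at the level of the student: "Outcomes measured include student accuracy on the TNEC HAZWOPER performance instruments including; 1) the 40 Hr HazWoper Course Workbook". Performance on these instruments is then compared by a t-test, and the unit of analysis is not stated.

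The same section reproduces several pages under the label of instrument. For Module 1 (Activity 3-A) the task reads "As a group, answer questions 1-3 using the following information". For Module 5 (Activity 3-B) it reads "Do not look up each chemical yourself. Have each group member look up a couple of chemicals, then share the results". For Module 2 (Activity 11-A) the text shown gives no group instruction: "Using the site map on page 15 and the job description below, answer the questions on the next page".

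On delivery, section 8.0 says of the intervention classes that "trainees will be provided with an Oculus VR headset to complete virtual reality modules based on activities covered in the TNEC 40 hour course workbook", and of the control classes that "trainees will complete all of the activities following standard practice which includes filling out sheets, reviewing 2D photographs, and reviewing slides". The standard workbook is used in both arms, and assessments follow the same sequence. The protocol gives no group size and no scoring rule. It does not say whether a sheet is scored per trainee or per group, or whether VR modules are done alone.

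**The concern.** A trainee who follows 3-A or 3-B as printed hands in answers that are partly or wholly other people's. This has two consequences.

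- **What is measured.** A pooled answer does not isolate what the individual trainee understood. Section 1.0 expects better comprehension among VR trainees, and the workbook is one of the few listed instruments that could yield an accuracy score to test this.
- **Precision.** Trainees who share an answer are not independent observations. A t-test that counts each of them separately gives a standard error that is too small and a p-value that is too low.

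Allocation is by course, so the sharing takes place within an arm. The harm is dependence and a blurred measure, and not leakage of the intervention into the control arm.

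**Working it through.** **1. The plan's own count.** Section 4.0 gives 6 VR and 6 control courses, with 15–25 people per class. 12 × 15 = 180 and 12 × 25 = 300, which matches the stated 180–300. Per arm this is 6 × 15 = 90 to 6 × 25 = 150. The plan gives no alpha, power, effect size or SD, so there is no power calculation to reproduce.

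**2. Which instruments carry a group instruction.**

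| Instrument shown in section 8.0 | Group instruction |
|---|---|
| Activity 3-A (Module 1) | Yes, answered as a group |
| Activity 11-A (Module 2) | None in the text shown; questions page not shown |
| Field exercise (Module 3) | No text shown |
| Visual Inspection Checklist (Module 4) | None |
| Activity 3-B (Module 5) | Yes, divided and shared |

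The count is two of five modules, or two of the three workbook activities reproduced. Sharing of results is printed in 3-B only.

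**3. How much of a 3-B sheet is the trainee's own.** The 3-B table has 10 chemicals. If a couple means 2 per member and each chemical is looked up once, the group has 10 / 2 = 5 members. Then 2 / 10 = 20% of the rows are the trainee's own and 80% come from others. No group size is stated, so groups of 3 to 5 are assumed below.

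**4. Effect on precision (illustration).** Assumptions not in the documents: group size g, one identical answer per group, two-sided alpha 0.05, 80% power, no further course clustering.

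- Independent answers per arm = n / g.
- Detectable standardized difference = (1.96 + 0.84) × √(2 / (n / g)).
- If the group answer is credited to every member, the variance of the arm mean is g times what the t-test assumes. Actual alpha = 2 × [1 − Φ(1.96 / √g)].

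| g | Independent answers per arm | Both arms | Detectable difference (SD) | Actual alpha |
|---|---|---|---|---|
| 1 | 90–150 | 180–300 | 0.42–0.32 | 0.05 |
| 3 | 30–50 | 60–100 | 0.72–0.56 | 0.26 |
| 5 | 18–30 | 36–60 | 0.93–0.72 | 0.38 |

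With partial agreement ρ the variance multiplier is 1 + (g − 1)ρ. At ρ = 0.5 it is 2 for g = 3 and 3 for g = 5, giving actual alpha of about 0.17 and 0.26. The inflation is smaller but still large.

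**5. Effect on the difference between arms (illustration).** Assume a true individual gain from 60% to 70% correct (10 points), independent members and binary items.

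- **Divided look-up, as 3-B is printed.** Each row is found by one member, so the expected table score is p: 60% v 70%. The 10 points are preserved, and the harm is dependence.
- **Any member who knows supplies the answer.** This is 1 − (1 − p)^g. For g = 5: 1 − 0.4⁵ = 99.0% v 1 − 0.3⁵ = 99.8%, or 0.8 points. For g = 3: 93.6% v 97.3%, or 3.7 points.
- **Majority answer.** For g = 5: 68.3% v 83.7%, or 15.4 points. For g = 3: 64.8% v 78.4%, or 13.6 points.

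With both arms pooled the sign is kept, but the size depends on a pooling rule that the protocol does not give.

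**The case against.** The strongest reply is that the problem is narrow. Section 1.0 states the overall objective as protocol adherence in hands-on field exercises, which two workbook pages do not touch. The self-report scales are unaffected. The Toxic Properties Activity is not reproduced, so its format is unknown. Because the same workbook is used in both arms, the natural reading is that the same group instructions apply to both, and 3-B's divided look-up leaves the expected difference unbiased. The opening note says that data collection instruments are submitted separately, so a scoring rule may exist elsewhere. The plan also intends to estimate an ICC in the pilot.

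Most of this stands and limits the scope. It does not remove the point. The group instructions are printed on pages the protocol itself labels as instruments, and a separate score sheet would not turn pooled answers into individual ones. Scoring each trainee's sheet after discussion would not do so either. The ICC is to be used to determine effect size; nothing says it will enter the t-test.

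A reader might infer that VR trainees answer alone while controls pool, so that the contrast could reverse sign. Under the step 5 assumptions that would give 70% − 99.0% = −29 points (groups of 5, any member knows) or 70% − 68.3% = +1.7 points (majority). The documents do not support this as a fact: a headset per trainee does not say how the answers are then formed. It remains a possibility that the protocol should close off.

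**Conclusion.** The point holds for Activities 3-A and 3-B. As printed, their scores are not individual accuracy and are not independent between groupmates, and a t-test on trainees would understate the error. In the illustration, a nominal 5% test on these items runs at about 26% to 38%, and the detectable difference rises from 0.32–0.42 SD to 0.56–0.93 SD. These figures rest on assumed groups of 3 to 5, identical answers within a group and no course clustering. A total workbook score that mixes in individually answered items would be affected less.

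A reader might also conclude that the workbook as a whole is answered in groups and cannot measure student accuracy. That goes too far: Activity 11-A, the Visual Inspection Checklist and the field exercise are not shown to be affected. Nor can a size of bias in the arm difference be stated, because the pooling rule is undocumented. The figures in step 5 are illustrations only.

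**What to change.** For 3-A and 3-B, in both arms and under the same conditions, have each trainee write their own answers on a coded sheet after the VR module or the paper and slide material, and before any group discussion or sharing. For 3-B, use a short fixed set of chemicals per trainee. Score only that sheet as student accuracy, then run the group activity as usual. This restores 90–150 individual answers per arm, before any allowance for course clustering. It must be settled before data collection, because individual answers cannot be recovered from pooled pages.

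The cost is one sheet and a few minutes per activity. Against module times of 1–5 minutes that is not trivial. Against the course it is small: if each sheet took 5 minutes (assumed), 2 × 5 = 10 of 40 × 60 = 2,400 minutes, or about 0.4%. A written attempt before discussion may also alter the discussion slightly, but equally in both arms.

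If individual sheets are not used, score these two activities once per group, do not describe them as student accuracy, and allow for group and course clustering in the comparison.

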## Instrument

3.1 CHEMICAL HAZARDS - 3 • Pg 38

### ACTIVITY 3-B USING THE NIOSH GUIDE: CHEMICAL PROPERTIES

**Purpose:** To learn to how to look up information in the NIOSH Pocket Guide to Chemical Hazards. To help students recognize when chemicals have hazardous properties.

**Task:** Using the NIOSH Pocket Guide, fill in the table on page 41. (Write "NA" if the chemical property does not apply.) Do not look up each chemical yourself. Have each group member look up a couple of chemicals, then share the results. Answer the following questions about each chemical.

[figure not shown]
1. Does the chemical present a fire/explosion hazard ?
2. Is the chemical likely to form high vapor concentrations ?
3. Is the vapor/gas lighter or heavier than air ?  
(Remember : the molecular weight of air is 29. See page 30.)
4. Do you have any other concerns about the chemical ?

[figure not shown]
Continued on the next page

3.1 Ch. 3 • Pg 39

#### ACTIVITY 3-B (continued)

Chemical	CAS#	Form (solid, liquid or gas)	Vapor Pressure (mmHg)	Molecular Weight	Flash Point (°F)	LFL (%)
Arsenic						
Toluene						
Methyl Ethyl Ketone						
Sulfuric Acid						
Acrylonitrile						
Ammonia						
Sodium Hydroxide						
PCB's						
Sodium Cyanide						
Perchloro- ethylene						

IMPRINT Intervention (Virtual Environment)
		

Control
	
Vapor Density
  
Flammable/Explosive Limits 9
 
 
▶ Lower explosive limit—the lowest percentage of fuel in air that will support combustion.
 
▶ Concentrations less than this percentage are “too lean” to support combustion.
 
▶ Upper explosive limit—the highest percentage of fuel in air that will support combustion.
 
  
Flammable Gas 15
 
 
▶ A gas that has a flammable range <math>\leq 13\%</math> or a flammable range <math>> 12\%</math>.
 
 	

## 9.0 Research with Vulnerable Populations

N/A

## 10.0 Incomplete Disclosure or Deception:

N/A

## 11.0 Consent Process:

Prior to enrollment in the study students and trainers will be presented with informed consent documentation. Informed consent will take place online or in the classroom. Storage of informed consent will be saved on a secure server used to host sensitive information where a password is required for entry and/or decryption or in locked cabinet file.

Students will have the opportunity to contact TNEC or the researchers directly with any questions prior to registering for the course and consenting to the study.

## **12.0 Research with Children – Parental Permission, Child Assent, and Other Considerations:**

N/A

## **13.0 Waiver of Participant Signature on Consent Form:**

N/A

## **14.0 Waivers and Alterations of Consent Information:**

N/A

## **15.0 Financial Compensation:**

Trainees will have the opportunity to be entered into a \$50 gift card raffle with the completion of the post course survey.

They will NOT receive any type of rights for discoveries, patents or products developed from this research.

There is no more than Minimal Risk to participants.

## **16.0 Audio/Video Recording/Photography**

N/A

## **17.0 Potential Benefits of this Research:**

No benefits are promised. Some benefits might include an improved training experience and improved retention of training concepts.

We anticipate trainees and classes assigned to the intervention will perform better than those who use standard paper and PowerPoint based activities. We believe their comprehension of topics will be greater, and it is likely that they will have a greater ability to recall HAZWOPER guidelines in the field. We

also anticipate after class survey results will indicate a better HAZWOPER training experience and increased levels of satisfaction with the course.

Long-term benefits of participation include improvement in retention of HAZWOPER guidelines when responding to Hazardous Material (HAZMAT) disasters. We anticipate trainees and classes assigned to the intervention will perform better than those who use standard paper and PowerPoint based activities. We believe their comprehension of topics will be greater, and it is likely that they will have a greater ability to recall HAZWOPER guidelines in the field. We also anticipate after class survey results will indicate a better HAZWOPER training experience and increased levels of satisfaction with the course.

## **18.0 Risks to Participants:**

There is a slight chance of injury through falling when walking or moving through the room during the tasks performed. There are additional risks when using virtual reality equipment or engaging in a virtual environment. These risks are infrequent, but may include motion sickness, disorientation, and dizziness. The experimenter will explain how you can take breaks during the experiment to prevent or relieve these potential risks, and you will be allowed to stop a task, and if necessary, exit the virtual environment by removing the virtual reality goggles at any time if you begin to feel discomfort or other undesirable sensations.

This research is no more than minimal risk. The level of risk is expected to about the same as risks of daily life or a working with protective equipment used throughout training.

## **19.0 Provisions to Protect Participant Privacy and Data Confidentiality:**

Data collection during training sessions will include written notes of observed activities, with a follow-up interview to gain greater context. A demographic survey will be administered at the end of each data collection session for all participants to collect information, such as age, sex, ethnicity, and race.

We will make every attempt to not collect identifiable data, but we will also review and de-identify all data. Participants will be assigned a unique, anonymous identifier linking them to their data. To protect participant confidentiality, all paperwork that could be directly linked to the participant personally (such as a signed consent form or payment documentation forms) will be stored in the investigators' locked filing cabinets. All other data will be de-identified (i.e., identified by code rather than with personal information) and stored in a locked cabinet (different from the cabinet where data that could be

linked personally to the participant is stored) or on a computer where a password is required for entry and/or decryption. The study data will be stored on a password protected and encrypted network storage drive that only the Principle Investigator and research team can access. This system is currently in use and has been used in previous studies for storage of human subjects study files. Only properly trained study staff who require data access for the purposes of completing the study will receive a password or key.

Data will be stored for 5 years and transferred through VPN secured server.

## **20.0 Data Monitoring Plan to Ensure the Safety of Participants:**

Data will be monitored monthly by the PI(s) given the frequency of the course. At that time the safety of equipment will be evaluated and VR Headsets will be cleaned.

## **21.0 Long-term Data and Specimen Storage and Sharing:**

We will make every attempt to not collect identifiable data, but we will also review and de-identify all data. Participants will be assigned a unique, anonymous identifier linking them to their data. To protect participant confidentiality, all paperwork that could be directly linked to the participant personally (such as a signed consent form or payment documentation forms) will be stored in the investigators' locked filing cabinets. All other data will be de-identified (i.e., identified by code rather than with personal information) and stored in a locked cabinet (different from the cabinet where data that could be linked personally to the participant is stored) or on a computer where a password is required for entry and/or decryption. The study data will be stored on a password protected and encrypted network storage drive that only the Principal Investigator and research team can access. This system is currently in use and has been used in previous studies for storage of human subjects study files. Only properly trained study staff who require data access for the purposes of completing the study will receive a password or key.

Data will be stored for 5 years and transferred through VPN secured server

